## **8. PARTICIPANT IDENTIFICATION**

### **8.1. Study Participants**

Patients scheduled for elective AF ablation in view of a history of symptomatic and drug-refractory paroxysmal AF.

### **8.2. Inclusion Criteria**

The participant must satisfy the following conditions:

- Males older than 40 years or females older than 40 and sterile or in post-menopausal age;
- willing and able to give informed consent for participation in the study;
- history of symptomatic and drug-refractory paroxysmal atrial fibrillation;
- planned AF ablation on a clinical basis.

### **8.3. Exclusion Criteria**

The participant may not enter the study if ANY of the following apply:

- age less than 40 years and more than 80 years;

Subject: Research protocol	Short Title: INSIDE PVs study	Chief Investigator: [name]
Ethics Ref:		
Version/Date: 1.0 /30 th June 2016	IRAS Ref: 156673	16/WM/0379
Page 14 of 29		

- pregnancy, trying for a baby or breast feeding;
- any other significant disease or disorder which, in the opinion of the investigator, may either put the participants at risk because of participation in the study, or may influence the result of the study, or the participant's ability to participate in the study;
- documented allergy to iodinated contrast medium; ;
- renal insufficiency (eGFR<30);
- weight exceeding the maximum load of the scanner (250kg).

## 9. STUDY PROCEDURES

### 9.1. Recruitment

Potential participants will first be approached some weeks before the AF procedure. Outpatient clinic letters of patients placed on the waiting list for catheter ablation of AF by the OUH NHS Trust Cardiac Rhythm Management team will be screened by a member of the research team to assess suitability for inclusion in the study. A letter of invitation, a patient information leaflet and a consent form will be given to potential participants at their routine clinic visits or sent by post at the time their procedure date is determined (usually a few weeks in advance). The participant will be allowed time to consider the information, and the opportunity to ask questions to the Investigator, their GP or other independent parties to decide whether they will participate in the study.

Once patients have had time to consider the information (and discuss with relatives, friends and their GP if they wish), they will be invited to contact a member of the study team who can discuss the study further. If they wish to take part, they will be approached at their pre-admission visit before the procedure (1-2 weeks before the AF ablation) for a baseline visit including informed consent, screening, eligibility assessment and pre-procedural cardiac CT imaging.

### 9.2. Baseline visit

#### 9.2.1. Informed Consent

Informed consent will be obtained by a qualified and experienced investigator who is familiar with the study protocol and procedures. This may be the chief investigator, a principal investigator, the research fellow or a research nurse. The list of eligible individuals will be specified in the delegation log.

Written versions of the Participant Information and Informed Consent will be presented to the participants detailing no less than: the exact nature of the study; what it will involve for the participant; the implications and constraints of the study and the benefits and risks involved in taking part. It will be clearly stated that the participant is free to withdraw from the study at any time without giving a reason or any prejudice to future care and rights.

Subject: Research protocol	Short Title: INSIDE PVs study	Chief Investigator: [name]
Ethics Ref:		
Version/Date: 1.0 /30 th June 2016	IRAS Ref: 156673	16/WM/0379
Page 15 of 29		

Written Informed Consent will then be obtained by means of participant dated signature and dated signature of the person who presented and obtained the Informed Consent. A copy of the signed consent form will be given to the participants. The original signed form will be retained at the study site. The participant must personally sign and date the latest approved version of the informed consent form before any study specific procedures are performed.

### **9.2.2. Screening and Eligibility Assessment**

It will include:

- a. demographics;
- b. exclusion of pregnancy or breast feeding in case of child-bearing age female;
- c. detailed collection of any relevant medical history;
- d. list of current medications and antiarrhythmic drugs previously taken.

### **9.2.3. Pre-procedural CT imaging**

As current practice, a pre-procedural cardiac CT scan will be performed to define the LA and PV anatomy and to measure the baseline LA wall thickness and PVs ostial diameters. The technical aspects of CT imaging are described in the intervention section.

## **9.3. AF ablation**

The patient will be admitted to the hospital on the morning of the procedure or on the night before the procedure, as per local SOP's. Apart from intra-procedural ICE/IVUS imaging, the AF ablations will be conducted in a completely standard fashion.

All AF ablations will be performed under general anaesthesia and on uninterrupted therapeutic anticoagulation with warfarin (target INR 2-3 in the last 3 weeks at least) or one of the new non-Vitamin K anticoagulant drugs. A heparin infusion will also be administered during the procedure with target Activated Clotting Time (ACT) values of 300-350 sec. Three-dimensional (3D) electro-anatomical mapping and/or fluoroscopy will be used by the operator, as usual, as anatomical guide during the procedure.

After general anaesthesia and oro-tracheal intubation, a trans-oesophageal echocardiogram (TOE) will be performed to rule out the presence of thrombus in the LA appendage.

Venous femoral access will be achieved and a deflectable decapolar diagnostic catheter placed to the coronary sinus. One or two atrial trans-septal punctures will be performed under TOE-guidance. The choice of the trans-septal kit (needle and sheath) and of the number of performed trans-septal punctures will be left to the operator.

Subject: Research protocol	Short Title: INSIDE PVs study	Chief Investigator: [name]
		Ethics Ref:
Version/Date: 1.0 /30 th June 2016	IRAS Ref: 156673	16/WM/0379
Page 16 of 29		

After the trans-septal puncture(s), pulmonary vein isolation (PVI) will be performed by using RF, cryo or laser energy as per operator's preference.

When using RF energy, the LA geometry will be reconstructed by using a 3-dimensional (3D) electro-anatomical mapping (EnSite Velocity or CARTO mapping system) and a multipolar circular mapping catheter (St Jude Medical Optima or Biosense Webster Lasso). Then a contact force ablation catheter (St Jude Medical EndosenseTacticath or Biosense Webster SmartTouch) through a deflectable sheath St Jude Medical Agilis will be used for PVI. The ablation sites will be annotated on the 3D electro-anatomical map. The choice of RF power, application time and mean contact force will be also left to operator preference.

When using cryo energy, LA and PV angiography will be performed in order to delineate their anatomy. A 11F FlexCath sheath (Medtronic, CA, USA) will be advanced to the LA and used to deliver either a 28 mm cryoablation balloon (Arctic Front Advance, Medtronic, CA, USA). The balloon will be inflated at the ostium of each PV. After retrograde PV angiography, used to demonstrate PV occlusion, one or two 180-seconds freezes will be performed in each PV until PV isolation is confirmed using PV mapping with an Achieve guidewire and exit block confirmed with pacing.

When using laser energy, a laser balloon system (HeartLight, CardioFocus) will be delivered to the LA through a 12-F deflectable sheath and inflated at the ostium of each PV. Ablation lesions will be delivered in a circumferential, contiguous, and overlapping manner around the PV using 5–12 W power. Pulmonary vein isolation will be confirmed using PV mapping with an Achieve guidewire (Medtronic, CA, USA) and exit block confirmed with pacing (5)Before and after PVs encirclement, ultrasound imaging of the PVs-LA junctions with ICE or IVUS will be performed as described in the intervention section.

A trans-thoracic echocardiogram will be performed at the end of the procedure to rule out the presence of pericardial effusion. Protamine will be administered to reverse heparin.

#### **9.4. Pre-discharge review**

As part of standard care, each patient will be reviewed the day after the ablation procedure, before discharge. The occurrence of any procedural complications will be investigated.

#### **9.5. Post-procedural CT imaging**

A post-procedural cardiac CT will be performed within 24h of the AF ablation to look at acute changes in LA wall thickness and PVs ostial diameters. The technical aspects of CT imaging are described in the intervention section.

#### **9.6. Telephone follow-up at 1 week**

As part of the research study, a telephone follow-up will be performed 1 week after the procedure to assess late-presentation procedural complications (i.e. acute cerebrovascular events as TIA or stroke, pericardial

Subject: Research protocol	Short Title: INSIDE PVs study	Chief Investigator: [name]
Ethics Ref:		
Version/Date: 1.0 /30 th June 2016	IRAS Ref: 156673	16/WM/0379
Page 17 of 29		

effusion, etc.). The patient's existing clinical care team will be informed about any symptoms and the decision to carry any additional investigations to investigate will be left to them.

The 1-week telephone follow-up will be the end of the study for each patient.

### **9.7. Image integration and data analysis**

The pre-procedural CT images and the post-procedural CT images will be compared for each patient.

Moreover, the pre and post-procedural CT images will be compared with the corresponding IVUS or ICE images. The plane of the circumferential ablation line will be identified by using PV branching as reference anatomical markers and it will be divided into 12 segments by using a clock-face model. The LA wall thickness will be measured at each segment and comparisons will be made between pre and post-ablation and between IVUS/ICE and CT at each timepoint.

The percentage changes in LA wall thickness after AF ablation will be compared between the three energy modalities (RF, cryo and laser).

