At the other end of the spectrum, deep lesions can potentially result in perforation and collateral damage. Cadaveric anatomical studies show that the LA wall thickness is extremely variable from subject to subject, from less than 1 to more than 7 mm. Even within individual patient, significant differences in the mean and maximum LA wall thickness exist among different areas that are often targeted during catheter ablation (15). This inter- and intra-patient regional variability has significant implications in determining the appropriate duration and intensity of energy delivered during catheter-based ablation procedures.

For these reasons, real-time information about LA wall thickness and morphological changes of the LA wall during energy delivery for ablation would be extremely useful to predict the achievement of permanent trans-mural lesions, to identify the possible causes of ablation failure and to avoid the occurrence of perforation and/or other collateral damage (16) .

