**Ethics Ref:**

16/WM/0379

**Version/Date:** 1.0 /30th June 2016    **IRAS Ref:** 156673

Secondary Objectives	Secondary Outcome Measure	
1. Feasibility of ICE/IVUS for real time imaging of the LA thickness and PV ostial diameters during AF ablation	1a. Additional procedural time 1b. Image quality	Day of AF ablation procedure
2. Comparison between acute tissue changes produced by RF, cryo and laser energy	2. Percentage change of LA wall thickness with each ablation modality (RF, cryo and laser energy)	Day of AF ablation procedure
3. Standardization of CT for LA wall thickness imaging with identification of a minimum dataset of acquisitions and reduction of radiation exposure	3. CT acquisitions associated to reproducible measurement of LA wall thickness with the lowest radiation exposure	Some days before and day after AF ablation procedure

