## 10. INTERVENTIONS

### 10.1. CT imaging

All cardiac computed tomographic (CT) studies will be performed using an Aquilion One scanner (Toshiba Medical Systems, Otawara, Japan), with 320 detector rows (each 0.5mm wide) and a gantry rotation time of 350ms. This allows the entire heart to be imaged in a single heartbeat, from carina to diaphragm, with a maximum of 16cm crano-caudal coverage. The electrocardiogram (ECG) will be monitored to allow prospective gating of image acquisition, with a phase window set to 30-80% of the R-R interval to allow assessment of left atrial wall thickness in both atrial diastole and systole. If necessary, metoprolol will be administered intravenously in a series of doses (to a maximum of 80mg) to achieve a heart rate of 60bpm. The lowest tube voltage (100kVp or 120kVp) will be used that delivers a small focal spot based on scout image attenuation, with automatic selection of tube current (200-500mA).

A power injection of intravenous iodinated contrast (Niopam 370, or equivalent) will be given via an intravenous cannula sited in an antecubital vein. A volume of 40-80ml will be used at an infusion rate of 4-6ml/s, depending on patient morphology. This will be followed by 50ml of normal saline given at a similar rate. A region of interest will be positioned within the descending aorta on a test slice, and when the Hounsfield units exceed 180 a breath-hold and image acquisition after a 3s delay will be triggered. Given uncertainty about the optimal way to image and measure the left atrial myocardium, after a delay of 40s, a second (“venous phase”) acquisition will be performed using the same parameters as the first.

Images will be reconstructed iteratively with soft and sharp kernels, with a slice thickness of 0.5mm and an increment of 0.25mm. Analysis will be performed on a dedicated post-processing workstation (Terarecon). The thickness of the left atrial wall will be measured at a number of locations and especially in correspondence of the circumferential ablation line, identified retrospectively by using PV branching as anatomical markers. Of note, measurements will be optimally standardized according to position, phase of the R-R interval and arterial versus venous acquisition as this is another important aim of this pilot study.

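### Percentage wall change is compared between operator-chosen groups of 4 without baseline adjustment, so a difference in baseline thickness could read as an energy effect

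*Combined protocol and SAP*

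**What the plan says.** Section 6 defines secondary outcome 2 as "Percentage change of LA wall thickness with each ablation modality (RF, cryo and laser energy" and times it on the day of the ablation. Section 9.7 repeats it as the only stated comparison of wall change between energies: "The percentage changes in LA wall thickness after AF ablation will be compared between the three energy modalities (RF, cryo and laser".

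For measurement, section 9.7 takes the plane of the circumferential ablation line and says "it will be divided into 12 segments by using a clock-face model". Thickness is read at each segment. The plan does not say whether the percentage is formed segment by segment or from patient means.

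On allocation, section 9.3 says "pulmonary vein isolation (PVI) will be performed by using RF, cryo or laser energy as per operator's preference", and section 12.1 plans 4 patients per energy. Section 12.2 names ANOVA for numerical variables and mentions no covariate.

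On baseline thickness, section 4.1 reports from cadaveric studies that "the LA wall thickness is extremely variable from subject to subject, from less than 1 to more than 7 mm", and adds: "Even within individual patient, significant differences in the mean and maximum LA wall thickness exist among different areas".

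**The concern.** A percentage change divides by the measured baseline. That causes two separate problems.

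- **Scale.** If swelling is roughly the same number of mm whatever the wall, thin walls give larger percentages. Nothing balances baseline thickness across three small, non-randomised groups and nothing adjusts for it, so a baseline difference can pass for an energy difference.
- **Reading error.** Error in the denominator does not average out. A mean of segment percentages can be positive when nothing has changed.

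Section 12.1 says the energy findings are to be taken into a larger randomised study. A distorted contrast here could carry over into that study's design.

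**Working it through.** **Inputs from the documents.** 12 patients, 4 per energy; 12 segments; ANOVA; energy chosen by the operator. The only figure to reproduce is 3 × 4 = 12. There is no power calculation and no expected percentage change.

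**Inputs assumed, because the documents give none.** Swelling of 0.5 mm; group mean baselines of 2 to 3 mm; reading-error SD of 0.1, 0.25 or 0.5 mm per measurement.

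**Step 1: scale.** Percentage change = 100 × d / b, for swelling d and baseline b.
- b = 2 mm: 100 × 0.5 / 2 = 25%.
- b = 3 mm: 100 × 0.5 / 3 = 16.7%.
- The gap is 8.3 points, a ratio of 1.5, with no difference in mm.
- Baselines of 2 and 2.5 mm give 25% and 20%, a gap of 5 points.

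**Step 2: chance imbalance alone.** Three groups of 4 were simulated with the same 0.5 mm swelling in every patient and a mean baseline of 2 mm. For between-patient SDs of 0.3, 0.5 and 0.7 mm, the expected gap between the highest and lowest group percentage is 3.5, 7.0 and 12.3 points. At a mean of 3 mm and SD 0.7 mm it is 4.2 points. This needs neither segment-level percentages nor reading error. Operator choice could add to it.

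**Step 3: reading error with no true change.** For independent errors of SD e, the mean of 100 × (post/pre − 1) is approximately 100 × (e/b)². For e = 0.25 mm:

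| True wall | Formula | Simulated |
|---|---|---|
| 1 mm | 6.25% | 7.4 to 7.8%, depending on how very small readings are handled |
| 2 mm | 1.56% | 1.6% |
| 3 mm | 0.69% | 0.7% |

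- SD 0.1 mm gives 1.05%, 0.25% and 0.11% at 1, 2 and 3 mm.
- SD 0.5 mm gives 18.6%, 7.9% and 3.1%. The first figure drops 8.8% of readings as unusable, so it depends on the cut-off.
- Averaging 12 segments before dividing reduces the error variance twelvefold. For e = 0.25 mm the formula gives 6.25 / 12 = 0.52% at 1 mm (simulated 0.53%) and 1.56 / 12 = 0.13% at 2 mm. Across the settings tried the bias stays below 0.6%, except 2.3% for SD 0.5 mm on a 1 mm wall.
- If pre and post errors are correlated at 0, 0.5 or 0.9, the segment-level bias at 1 mm (SD 0.25 mm) is 7.6%, 3.7% or 0.7%.

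Between groups at 2 and 3 mm, the SD 0.25 mm bias differs by only 1.6 − 0.7 = 0.9 points, against 8.3 points from scale. Scale is the larger problem for the energy comparison.

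**Step 4: does a baseline covariate help?** Fixed swelling is change = 0.5 + 0 × b. Proportional swelling of, say, 20% is change = 0 + 0.2 × b. Both are straight lines in b, so one model with baseline as covariate contains both. In a simulation with assumed group baselines of 2, 2.5 and 3 mm and no energy difference, nominal 5% tests behaved as follows:
- percentage ANOVA rejected 17% of the time under fixed swelling;
- unadjusted change in mm rejected 22% under proportional swelling;
- change in mm with the covariate stayed near 5% under both.

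The two inflated rates move with the assumed scatter between patients. The pattern is what matters.

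**The case against.** The strongest objection is that percentage is the right scale if swelling is proportional to thickness. A 20% swelling is 0.4 mm on a 2 mm wall and 0.6 mm on a 3 mm wall, so unadjusted change in mm would mislead in the opposite direction. This stands against swapping the percentage for plain mm change. It does not stand against a baseline-adjusted analysis, which accommodates either case.

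Sections 12.2 and 12.3 plan comparisons and summaries at each time point, so baseline thickness by energy would probably be reported. That would show an imbalance but not remove it.

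This is also a secondary outcome in a pilot that promises only some insight into energy differences. That limits the weight of the point.

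A reader might go further in four ways that the documents do not support:
- **A seven-fold distortion.** The range from under 1 to over 7 mm is cadaveric and between subjects. No range is given at the ablation line, and means of groups of 4 will spread far less.
- **Reading error by itself creates an apparent rise.** This needs averaging over segments and largely independent errors. The plan states neither, and it gives no reading error.
- **CT resolution sets that error.** Section 10.1 describes a scanner "with 320 detector rows (each 0.5mm wide", but section 6 times this outcome on the day of ablation. Table 1 puts the second CT 12 to 24 hours later. The timing points to ICE/IVUS.
- **Any finding of oedema is undermined.** Section 9.7 separately compares thickness before and after ablation, and that comparison is not tied to percentages.

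**Conclusion.** The concern holds in a conditional form. The only stated energy comparison of wall change uses a ratio to baseline, in small groups that are not balanced on baseline and with no adjustment for it. If swelling is closer to a fixed amount than to a fixed proportion, a thinner-walled group could appear to swell more. The size is about 8 percentage points for assumed group baselines of 2 and 3 mm and 0.5 mm of swelling. The documents do not say which form swelling takes.

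The reading-error bias is a lesser addition. It matters only for segment-averaged percentages with largely independent errors, and most in thin walls. A bias common to all energies cancels between groups unless baseline thickness or reading error differs. The level of calculation should still be stated, because the plan leaves it open and the size of the bias depends on it.

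**What to change.** In sections 6, 9.7 and 12 (and the matching synopsis row):

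1. Compare energies on each patient's mean change in wall thickness in mm, measured by ICE/IVUS in line with the timing given for this outcome, with that patient's mean baseline thickness as covariate.
2. Keep the percentage as a descriptive result, computed per patient as mean post over mean pre thickness and not as an average of segment percentages.
3. Show baseline thickness by energy beside it.

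**Cost.** Wording only, with no new data. The formal comparison moves from % to mm. The residual degrees of freedom fall from 12 − 3 = 9 to 8. Some confounding will remain, because the groups are small and non-randomised and the baseline covariate is itself measured with error. The result should be labelled exploratory.

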### **9.8. Discontinuation/Withdrawal of Participants from Study**

Each participant has the right to withdraw from the study at any time. In addition, the Investigator may discontinue a participant from the study at any time if the Investigator considers it necessary for any reason including:

- Ineligibility (either arising during the study or retrospectively having been overlooked at screening)
- Significant protocol deviation
- Significant non-compliance with study requirements
- Withdrawal of Consent
- Loss to follow up

No specific procedures or observations will be required in case of discontinuation/withdrawal of participants from study rather than standard medical care.

The reason for withdrawal will be recorded in the CRF.

In case of withdrawal from the study in an early stage (before the study interventions), the patient data will be excluded from the analysis and a new participant will be enrolled.

In case of withdrawal from the study during the follow-up period, neither exclusion of the data of that participant from analysis nor replacement with a new participant will be required.

